The proposed interventions will target female patients in a family practice-based research network who are 50 to 75 years of age, nonadherent to current CRC screening recommendations, and may or may not be adherent to BC screening. Nonadherence to CRC screening recommendations is defined as not having had one of the recommended screening tests (fecal occult blood test, fecal immunochemical test, sigmoidoscopy, or colonoscopy) in the appropriate timeframe.⁽¹²⁾ A review of records for 180,000 women in the targeted age group and practice plan found that 26% were nonadherent to CRC screening guidelines but were adherent to BC guidelines, 44% were nonadherent to both CRC and BC screening guidelines, 10% were adherent to CRC but

not to BC screening guidelines, and 20% were adherent (currently up-to-date) to both screening guidelines. Because the group that is adherent to CRC but not BC screening is so **small (10%)**, we will not have power to sufficiently test interventions with this group. However, some women who may be at higher risk for CRC because of family history will likely be included in the study because family history data is not readily available in the medical records. At baseline interview and during the intervention, these women will be considered at higher than average risk for CRC and colonoscopy will be recommended.

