B.1. Prospective randomized trials have demonstrated that routine screening for both BC and CRC significantly reduce cancer mortality. Mortality and incidence for CRC and BC are higher than for any other cancers among nonsmokers in the United States.⁽¹⁸⁾ In 2009, approximately 24,680 women are expected to die from CRC and 40,170 women are expected to die from BC.⁽¹²⁾ Timely and routine screening is our best weapon against both CRC and BC mortality. Prospective randomized trials have demonstrated the efficacy of screening with fecal occult blood tests (FOBT) in reducing CRC mortality by over 30%.⁽¹⁹⁾ The removal of precancerous (adenomatous) polyps in the colon and rectum at the time of endoscopic screening has been found to decrease CRC incidence by 75% to 90%.⁽²⁰⁾ Additionally, mammography screening has been demonstrated to decrease mortality through early detection in randomized prospective trials conducted over the last 30 years. Eight major randomized controlled studies have collectively included more than 500,000 women in screening studies.⁽²¹⁻³⁴⁾ Women 50 or over who are routinely screened by mammography demonstrate a 30% reduction in mortality.

B.2. Screening for both CRC and BC is recommended for women 50 or older. Current guidelines for CRC screening recommend starting at age 50 and include 7 different test options for average-risk individuals, including: 1) annual FOBT, 2) annual fecal immunochemical test (FIT), 3) stool DNA test (sDNA), 4) flexible sigmoidoscopy every 5 years, 6) colonoscopy every 10 years, 6) double contrast barium enema every 5 years, or 7) CT colonography (virtual colonoscopy) every 5 years.^(1, 35) For persons at increased risk for CRC, screening colonoscopy is recommended.⁽³⁾ Although out-of-pocket cost varies by insurance plan, all insurers of women in this study include colonoscopy coverage for those at average or increased risk.

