D.2. Eligibility Criteria. Women will be considered eligible if they: 1) have been a patient of any of the participating physicians 2) ages 50 to 75; and 3) nonadherent to CRC screening guidelines and 4) have high speed Internet access. Exclusion criteria are: 1) having a personal history of colorectal cancer, colorectal polyps, or inflammatory bowel disease, and 2) having any medical conditions that would prohibit a mammogram or CRC screening. We are excluding women at high risk due to the exclusion criteria above which can be obtained through medical records. However, there will be women at higher than average risk for CRC due to family history that will likely be entered into the study. We will obtain the information about family history during the baseline interview and it will be considered through the intervention. Women at higher than average risk because of family history will be encouraged to have a colonoscopy.

Nonadherence to CRC screening guidelines will be defined as having had neither: 1) a fecal occult blood test in the last 12 months; or 2) a fecal immunochemical test in the past 12 months; or 3) a sigmoidoscopy more than 5 years ago; or 4) a colonoscopy more than 10 years ago. The algorithm for training research assistants to determine eligibility/adherence at baseline for CRC is included in **Appendix A**.

Table 1. Timeline

Activity	Year 1				Year 2				Year 3				Year 4				Year 5			
	Q1	Q2	Q3	Q4																
Intervention Development	X	X	X	X																
Refinement of process and outcome measures		X	X																	
Development/testing of study databases		X	X																	
Training research staff	X	X	X																	
Intervention pre-testing	X	X																		
Participant Enrollment		X	X	X	X	X	X	X	X	X	X	X	X	X	X	X				
Baseline data collection & intervention delivery		X	X	X	X	X	X	X	X	X	X	X	X	X	X	X				
4-week follow-up interview		X	X	X	X	X	X	X	X	X	X	X	X	X	X	X				
6-month follow-up interviewed med record audit			X			X	X	X	X	X	X	X	X	X	X	X	X	X	X	
Data cleaning and analyses													X	X	X	X	X	X	X	X
Analysis, write-up, dissemination																	X	X	X	X
Quality Assurance			X	X	X	X	X	X	X	X	X	X	X	X	X	X	X			

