months will be in **Group B**. Although there is a small group of women who could be adherent to CRC screening but not to BC screening (10%), the numbers are too small to have adequate power for testing hypotheses. In practice, however, the program can be easily modified to also accommodate women who are adherent to CRC but not to BC screening. Because administrative data may not include complete screening history information, adherence to CRC and BC screening guidelines will be verbally verified with each woman prior to consent to

determine eligibility. This will allow us to screen out women who are ineligible because they have received CRC or BC screening within the appropriate timeframe. The study timeline is illustrated in **Table 1**.

A minimum age of 50 was selected to allow women time for screening after they turned 50. If a woman develops CRC or BC during the study, she will no longer be a candidate for routine screening and her data will be deleted from final analysis. In our past work, this occurred only 2-4 times over the course of any given project. Claims data will verify initial eligibility regarding age and CRC and/or BC screening status followed by verbal confirmation at time of enrollment.

D.3. Sample. In the *Power Analyses* section, we show that inclusion of **397** participants in each of the four intervention groups - usual care, TIWeb, CSC, and TIWeb plus CSC - will yield adequate power to detect clinically significant effects at 6 months. The sample size also takes into account the average rollover of women to different health care plans that may occur during the course of this study. Women members are approximately 81% Caucasian and 19% African American. Letters of support for all sites are included in the consortium agreement section.

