*Consistency in intervention delivery is assured through the standardized programming used in the computer-assisted CSC and through taping and review of CSCs. The TIWeb guide the participant through all sections. The CSCs will be continuously recorded for quality assurance. Monthly taping of at least one TIWeb technical assistance session and T1, T2, and T3 interview for each interviewer will allow checks on consistency of performance. Taped interviews and CSC calls will be evaluated based on a checklist contained in **Appendix A**. Research assistants who are not delivering calls as instructed will be given additional training. Research assistants will address any unusual happenings during biweekly meetings. Decisions to modify procedures will be made jointly and documented. The research team will meet monthly to discuss any concerns with implementation of the protocol or collection of interview data. The principal investigators will meet weekly to refine the protocol and training procedures and to discuss ongoing issues.*

Table 6. Measurement of Outcomes: Stage and Adherence for BC and CRC

Stage	CRC Screening Average risk woman	CRC screening At higher risk because of family history	BC Screening
Precontemplation	Is nonadherent to national guidelines and does not intend to have one of the test options in next 6 months	Never had a colonoscopy or had one > 10 years ago and does not intend to have one in next 6 months	Never had a mammogram or had one \geq 15 mo. ago and does not intend to have one in next 6 months
Contemplation	Is nonadherent to national guidelines but intends to have one of the test options in next 6 months	Never had a colonoscopy or had one > 10 years ago and intends to have one in next 6 months	Never had or had mammogram more than 15 months ago but intends to have one in next 6 months
Action (Adherence to any CRC screening)	Had one of the test options since intervention	Had one of the test options since intervention	Had a mammogram since intervention
Action (Adherence to risk appropriate CRC screening)	Had one of the test options since intervention	Had a colonoscopy since intervention	Had a mammogram since intervention

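### Section D.2 words the sigmoidoscopy and colonoscopy parts of CRC nonadherence backwards, so read literally it admits up-to-date women and turns away overdue ones

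*Combined protocol and SAP*

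**What the plan says.** The operative definition is in section D.2. It opens "Nonadherence to CRC screening guidelines will be defined as having had neither" and lists four items. Items 1 and 2 are a fecal occult blood test and a fecal immunochemical test, each within the past 12 months. The list then continues "or 3) a sigmoidoscopy more than 5 years ago; or 4) a colonoscopy more than 10 years ago". The next sentence points to an appendix: "The algorithm for training research assistants to determine eligibility/adherence at baseline for CRC is included in" Appendix A.

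Other places bear on the same definition:

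- Section A (Specific Aims): "Nonadherence to CRC screening recommendations is defined as not having had one of the recommended screening tests", followed by the qualifier that the test must fall in its appropriate timeframe.
- Section B.2 gives the guideline intervals: "flexible sigmoidoscopy every 5 years, 6) colonoscopy every 10 years".
- D.2, in the paragraph on verbal verification, says the check will "screen out women who are ineligible because they have received CRC or BC screening within the appropriate timeframe".
- Table 6, family-history column, describes both pre-action stages with the words "Never had a colonoscopy or had one > 10 years ago".
- D.12 takes all enrolled women to be nonadherent to CRC screening at baseline.
- D.4 says that nonadherence for eligibility is determined as D.2 defines it.

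**The concern.** Items 1 and 2 name current tests; items 3 and 4 name lapsed ones. Placed under a single negation, the endoscopy items do the opposite of what the rest of the protocol intends. D.2 is also the only place that sets eligibility intervals test by test, so a reader sent there by D.4 finds the reversed rule.

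Three things would follow if the text were applied as written.

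1. Overdue women, who belong to the target population, would be turned away.
2. Women with no CRC test due would be enrolled. D.13 allows only two baseline stages, precontemplation and contemplation. In Table 6 both require the woman to be nonadherent (average risk) or to have no colonoscopy within 10 years (family history). A woman with a recent colonoscopy would have no baseline stage, so the stage-advancement outcome of Hypothesis 1 would be undefined for her.
3. Differences between arms in adherence would probably be diluted. The size is uncertain, because in Table 6 an average-risk woman reaches the action stage on "Had one of the test options since intervention", and an up-to-date woman could still do that.

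**Working it through.** **Logic check.** Cross stool test in the past 12 months (yes, no) with sigmoidoscopy (never, within 5 years, over 5 years ago) and colonoscopy (never, within 10 years, over 10 years ago). This gives 2 × 3 × 3 = 18 histories. Compare D.2 as written with the section A rule, using the section B.2 intervals. They disagree in 6 histories, all without a current stool test:

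| Sigmoidoscopy | Colonoscopy | Sections A and B.2 | D.2 as written |
|---|---|---|---|
| never | within 10 y | not eligible | eligible |
| within 5 y | never | not eligible | eligible |
| within 5 y | within 10 y | not eligible | eligible |
| never | over 10 y | eligible | not eligible |
| over 5 y | never | eligible | not eligible |
| over 5 y | over 10 y | eligible | not eligible |

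If the negation governs only items 1 and 2, the disagreement grows to 10 of 18, and a woman with a recent colonoscopy and no stool test is still admitted.

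**The plan's own power figures.** Inputs from D.12: adherence of 20%, 30%, 40% and 55% in arms 1 to 4 (usual care, TIWeb, CSC, both) and 357 per arm at 6 months. Two-sided α = 0.05 is assumed, because D.12 does not state it. Pooled two-proportion power is 0.871 for 1v2 (plan .87), 0.801 for 2v3 (plan .80) and 0.981 for 3v4 (plan .98). The other pairs exceed 0.99. None of these depends on the D.2 wording.

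**Illustration if the literal text were used.** Section A's record review gives 26% nonadherent to CRC only, 44% nonadherent to both, 20% adherent to both and 10% adherent to CRC only. Let s be the share of CRC-adherent women who are current through endoscopy alone. The documents do not give s; I take 0.5 to 0.9. Women wrongly turned away are ignored.

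- Group A: 0.20s / (0.26 + 0.20s) = 0.278 to 0.409
- Group B: 0.10s / (0.44 + 0.10s) = 0.102 to 0.170
- Overall at the 30/70 enrolment ratio in D.12: c = 0.3 × A + 0.7 × B = 0.155 to 0.242, or 246 to 384 of 1588

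Let u be these women's uptake relative to the planned rates. Each arm's rate is multiplied by 1 − c(1 − u):

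| u | 10-point difference becomes | 1v2 | 2v3 | 3v4 |
|---|---|---|---|---|
| 1 | 10 | 0.871 | 0.801 | 0.981 |
| 0.5 | 9.2 to 8.8 | 0.834 to 0.811 | 0.752 to 0.722 | 0.963 to 0.948 |
| 0 | 8.5 to 7.6 | 0.791 to 0.735 | 0.697 to 0.632 | 0.934 to 0.888 |

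D.13 plans a yes/no covariate for earlier endoscopy. If it separated the up-to-date women completely, then at u = 0 the effective size is 357(1 − c) = 302 to 271 per arm, and 2v3 power is 0.732 to 0.685.

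**The case against.** The strongest reply is that this is an editorial slip whose intent is plain. The eligibility list in D.2 itself requires nonadherence to guidelines. The verbal-verification paragraph, also in D.2 and therefore part of what D.4 cites, states the intended rule. Claims data, physician review of the lists and a screening questionnaire stand between the text and enrolment, and Appendix A may be correct. All of that is fair, and it is why no wrong enrolment is alleged. It does not remove the contradiction: D.2 then holds two incompatible rules, and only the reversed one carries test-by-test intervals. If the recruitment tools copied the wording, those checks would not necessarily catch it.

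The supporting passages are also uneven. Table 6 contradicts only the colonoscopy item, and only in the family-history column. Section B.2 is background. The sigmoidoscopy reversal is shown by combining sections A and B.2. These limits stand.

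The power illustration is open to more criticism. It rests on an assumed endoscopy share and assumed uptake. It leaves out overdue women lost from the pool, and it does not remove up-to-date women whom the polyp exclusion, or an additional old endoscopy, would bar. These omissions pull in opposite directions, so the range is not a bound. The initial test in D.13 is the 2×4 chi-square; even in the worst case shown its power stays above 0.999. The pairwise figures matter only because D.12 claims 80% power for every pair and 2v3 has no margin.

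**Conclusion.** The concern holds. As written, items 3 and 4 of D.2 reverse the endoscopy part of the nonadherence definition and conflict with sections A and B.2, the verbal check in D.2, Table 6 and the baseline premise in D.12. That conclusion follows from the text and needs no assumption.

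The effect on the trial is conditional. It arises only if recruiters or the database query followed the literal wording, which the supplied documents neither show nor rule out. The power loss is illustrative and depends on the assumed endoscopy share and uptake. The number of overdue women turned away cannot be sized, because the documents give no figure for lapsed endoscopy. This should be fixed because the sentence decides who enters the trial.

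**What to change.** Reconcile items 3 and 4 of D.2 with sections A and B.2, the verbal-verification paragraph and Table 6, so that one definition applies the protocol's own interval to each test. Then check the Appendix A algorithm, the screening questionnaire and the query that builds the recruitment lists against it.

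Only if that check finds women enrolled under the literal wording: identify them, state how their baseline stage is coded, and add a sensitivity analysis that leaves out those up to date at baseline.

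The cost is a few words in D.2 and a check of three recruitment tools. Sample size and design are unaffected.

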Women randomized to CSC will receive a telephone counseling call during which the opportunity to complete CRC screening (FOBT or a colonoscopy) and/or mammography will be offered. The CSC will include tailored counseling as well as the ability to schedule BC and CRC screening tests. The combined TIWeb + CSC group will receive a mailed TIWeb followed in four weeks by a CSC with the same opportunity to receive FOBT kits or schedule a colonoscopy and/or mammogram. The nurse counselor, knowing the participant is a good candidate for screening tests, will be trained to schedule CRC or BC screening appointments or to mail FOBT kits to individuals in the intervention groups even if they have not had a recent clinic visit. The usual care group will receive usual care that varies dependent upon the practice setting. Participants will have a baseline telephone or electronic survey prior to randomization that assesses beliefs, knowledge, self-reported CRC & BC screening, and other study variables. Four weeks following intervention, participants will be surveyed via

telephone or electronic survey on CRC & BC beliefs, knowledge, and participant involvement in and satisfaction with the intervention. Again at 6 months, a final telephone or electronic survey will be done and claims data collected. (See Figure 2) A Community Advisory Board will be involved in design and review of interventions, accrual, and intervention delivery.

In order to tell whether or not the two week opt out period is sufficient time for women to opt out, the PI and project manager will monitor a spreadsheet that will be developed for tracking calls made by study staff to women who indicate that they did opt out of the study by returning the refusal postcard, calling the toll free number, or emailing the project manager. If a woman indicates that she did opt out the study staff will apologize and indicate to the project manager or PI that this has happened. The project manager will then make sure her documentation is destroyed. Once this occurrence has happened a total of ten times, the PI will reevaluate the opt out time period and consider revising. Any occurrences will be reported to the IRB at continuing review.

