
who have not in **Group B**. The RA will also review the entire study verbally with the potential participant. Women will be referred to the introductory letter that indicates what study involvement includes. If a woman agrees to participate, the RA will obtain verbal consent for the study and conduct a baseline telephone interview immediately or schedule a more convenient time within one week. If she would like to complete the baseline interview electronically, she will be given instructions on how to do that. HIPAA documentation for release of medical records will be accessed and signed electronically at the time of the second online questionnaire. The woman will be able to review the electronic forms before indicating her signature. She will be able to print off the form as well. If a woman declines participation, she will be thanked for her time. We will need a cohort of approximately 45 women consented each month for 36 months to accrue a total of 1588 women. Assuming 50% will agree to participate, we will actually contact approximately 90 women each month.

Summary:

- 1) A list of eligible women will be pulled from databases and sent to the research study office at IUSON. The list will then be forwarded to the co-investigator in charge of recruitment ([name], Executive Director for the Indiana Family Practice Research Network), and the physician at each recruitment site will have the opportunity to review the list. Data will include name, address, DOB/age, and phone number as well as mammogram status. Each woman mailed an informational letter about the study and brochure. If the woman has not declined in two weeks, the woman's name will be added to the recruitment call list.
- 2) Trained RAs at the Center for Survey Research will begin call attempts to those women who had not opted out of the study.

- a. The RA will attempt 10 calls
- b. The call attempts will be logged on a call sheet.

If the woman is reached, the RA will verify eligibility using the screening questionnaire.

- 3) The RA will also review the entire study by reading the study information sheet over the phone, ask if she is interested in participating, and conduct a baseline interview at that time (or within 1 week if it's not a convenient time) if she agrees to participate in the study and gives verbal consent for the study.
 - a. If she does not want to participate, she will be thanked for her time and her information will be destroyed.

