- 4) After a woman provides verbal consent over the phone, she will be prompted to do the electronic HIPAA form at the time of the second online survey.
- 5) Once the consent and authorization are given, the woman is eligible for the rest of the study.
 - a. A reminder call will be made if the first online survey is not completed within 2 weeks. A refusal postcard will be sent if she cannot be reached.
- 6) Depending on the randomization of group:
 - a. Those receiving TIWeb only, the TIWeb information will be mailed and emailed out within 1 week of receiving the consent and authorization.
 - b. Those receiving the cancer screening call, the RA will begin attempting 1 week after receiving the consent and authorization.
 - c. Those receiving the TIWeb and call, the TIWeb information will be mailed and emailed within 1 week of receiving the consent and authorization. The call will then be attempted 1 week after the mailing of the TIWeb information.
- 7) Data collection calls or electronic communications will be placed at 4 weeks and 6 months following the intervention by the Center for Survey Research in Bloomington.
- 8) Information will be stored in locked file cabinets in a locked research office and data stored on a database that is password protected. This database will be used for this study only.

D.5. Data Collection. The baseline interview by phone or electronic communication, which will occur during the verbal consent call or within 1 week if the women needs a more convenient time, will include questions about CRC and BC screening as well as questions for perceived risk, benefits, barriers, and self-efficacy. Sociocultural/demographic variables will be measured for subgroup comparisons. The computer program used to conduct telephone surveys will have the randomization scheme integrated into the program. When a baseline survey is completed, the computer program will provide the randomized group assignment to the research assistant. The research assistant will then provide instructions to the participant based on her randomized group assignment.

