Program Effectiveness: The main effect is screening compliance at 6 months from the baseline measure as determined by the randomized trial. For those in **Group A**, CRC screening is the outcome. For **Group B**, there are three outcome groups: CRC screening adherence, BC screening adherence, and adherence to CRC and BC screening. Outcomes will be determined with an “intent-to-treat” analysis by analyzing data from all women who originally consented and were randomly assigned to a research arm regardless of deviations from the protocol, the degree of treatment they received (e.g., regardless of whether TIWeb was viewed or CSC was made), or withdrawal from treatment or loss to follow-up. The use of claims data and medical records data for the main outcome of adherence will make it possible to analyze adherence at 6 months even for women who dropped out, as long as claims data for those women can be obtained.

Program Costs: To calculate the costs of the interventions, we will consider delivery costs only. Costs associated with research and development (R&D) activity or costs of screening tests are excluded. The cost of developing the TIWeb is expected to be a major pre-intervention R&D cost. Researchers have debated how to handle these “first-copy” costs and there is no universally accepted “correct” answer. First-copy costs, defined as costs incurred in establishing a regimen or intervention, are considered quasi-fixed costs independent of the number of units produced, once production is started. Generally, first-copy costs are excluded when they involve situations in which much of the intervention is already in existence and only modification is needed to adapt it for implementation. While R&D costs can be high, they are “sunk cost” from a societal perspective, in any future decision to implement the interventions. The final product developed for this study could be made available to

other organizations. We expect managed care organizations would not develop their own TIWeb, but would rely on public access or licensing arrangements to secure such educational material. However, the cost of developing the TIWeb will be calculated to inform future developers of the approximate cost of developing this type of interactive technology for health promotion interventions and to test CE analysis with and without these costs.

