- **Missing data and methods for handling in analyses:** Missing data should be minimized by the use of telephone data collection and through interviewer training. Based on our previous work, we expect no more than 1-2% missing data for any single variable. Missing data for the major variables of CRC and breast cancer screening adherence (claims data) will be of concern if a woman changes health insurance plans. If a woman changes plans, we will still collect 6-month self-report data and inquire as to whether she has received either CRC or BC screening at another location. Because enrolled women will have signed informed consent to access claims data, we will be able to obtain CRC screening mammography records even in the event that health care plans have changed. We will examine reasons for drop-out and compare baseline characteristics of those with complete data versus those with missing data. If data are 'missing at random' (MAR) estimates will be biased and if 'missing completely at random' (MCAR) estimates will be inefficient if models are not adjusted for missingness. Therefore, we will use multiple imputation to perform adjustment for missingness. We will also perform sensitivity analyses to see how the results might have been affected under various assumptions had the data been available. The sensitivity analysis will also include estimating models while stratifying on the categories of missing data patterns,⁽¹⁴⁹⁾ although the multiple imputation method will be considered the more authoritative adjustment. Because patients will be randomized after they receive their baseline assessment, there are three possible missing data patterns (i.e., missing 2-week assessment, missing 6-month assessment, or missing both 2-week and 6-month). Furthermore, claims data will make it

possible to analyze adherence at 6 months even for women who dropped out, as long as claims data for those women can be obtained.

- **Sample bias:** We conservatively estimate that about 50% of contacted women will consent to participate, and women who are interested in CRC or BC screening may self-select into the study. Contacting only nonadherent women will minimize this bias.

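### Medical-record authorization is signed after the arm is disclosed, so some randomized women may have no authorized record-based outcome, contrary to the premise of the missing-data plan

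*Combined protocol and SAP*

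**What the plan says.** **When the authorization is signed.** The D.4 text puts it here: "HIPAA documentation for release of medical records will be accessed and signed electronically at the time of the second online questionnaire". Item 4 of the D.4 summary repeats this: after verbal consent by telephone, "she will be prompted to do the electronic HIPAA form at the time of the second online survey". Neither place says which survey is meant.

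**When the arm is released.** D.5: "When a baseline survey is completed, the computer program will provide the randomized group assignment to the research assistant". The next sentence reads: "The research assistant will then provide instructions to the participant based on her randomized group assignment". D.5 goes on to list what women in each arm are told to expect.

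**When the intervention starts.** Item 5 of the D.4 summary says: "Once the consent and authorization are given, the woman is eligible for the rest of the study". Item 6 then times delivery from receipt of the consent and authorization. D.8 times delivery from the baseline survey, and D.7 times the call-only arm from randomization.

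**What the analysis relies on.** In D.13, the Program Effectiveness paragraph defines intent-to-treat as all women who consented and were randomized. It says that claims and records make it possible "to analyze adherence at 6 months even for women who dropped out", on condition that the claims data can be had. The loss-to-follow-up bullet says, without that condition, that the primary outcomes can be read from an audit of electronic records. The missing-data bullet reasons: "Because enrolled women will have signed informed consent to access claims data", and concludes that records can be obtained even after a change of health plan.

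**The concern.** The analysis sections treat record access as settled for every enrolled woman. The recruitment and data-collection sections describe an order in which it is not. A woman is randomized and told her arm on verbal consent alone, and the release for her records comes later.

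Two things are at stake. First, the women for whom records matter most are those who stop answering surveys, and they are also the likeliest not to have signed. For fecal occult blood tests the gap matters more, because D.11 says these need a chart audit to verify. Second, signing becomes a decision made after randomization with the arm known. A woman told to expect only data-collection calls may weigh the form differently from one who has been offered a website or a nurse call. If signing differs by arm, the women with an authorized record-based outcome are no longer a randomized comparison.

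**Working it through.** **1. The order of events.** D.1, D.5 and Table 7 describe three surveys: baseline, 4 weeks and 6 months. D.1 describes the one after baseline: "Four weeks following intervention, participants will be surveyed via" telephone or electronic survey. Two readings of the second online questionnaire are open.

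- *It is the 4-week survey.* The order is then verbal consent, baseline, arm disclosed, intervention, authorization. A woman lost in the first weeks never signs. The nurse's review of records before the call (D.6.4) would also come before the authorization.
- *It is a separate step before the intervention,* as items 5 and 6 of the D.4 summary suggest. The order is then verbal consent, baseline, arm disclosed, authorization, intervention. A woman who does not sign has still been randomized and told her arm.

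The arm comes before the signature on both. The order reverses only if the second questionnaire is part of the baseline and precedes release of the assignment. No section describes such a survey.

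**2. The plan's own figures.** D.12 enrols 397 per arm and allows 10% attrition: 397 × 0.90 = 357.3, given as 357. The documents state no alpha for the power table; I assume two-sided 0.05. Power = Φ{[|p1 − p2|√n − 1.96√(2p̄(1 − p̄))] / √(p1(1 − p1) + p2(1 − p2))}.

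For the weakest pair, 30% against 40%: [0.10 × 18.894 − 1.96 × 0.6745] / 0.6708 = 0.846, so power is 0.801 (stated .80). The pairs 20% against 30% and 40% against 55% give 0.871 and 0.981 (stated .87 and .98). Loss within the 10% allowance therefore costs none of the stated power.

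**3. How many women.** The loss-to-follow-up bullet plans for 10% and expects about 5%, in total over 6 months. Women lost before signing are a subset, so the range is 0 to 10%: 0 to 397 × 0.10 = 39.7, about 40 per arm. Women who stay but decline to sign are not in that figure. The documents give no rate for them, and they keep their self-report.

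**4. What unequal signing could do (illustration; the loss rates are assumed).** Let true adherence be 20% in two arms. In the intervention arm all the women lost are nonadherent; in usual care the loss is random. Observed intervention-arm adherence is 0.20 / (1 − m).

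- Loss of 0% in usual care and 5% in the intervention arm: 0.20 / 0.95 = 21.1%. With 397 and 377 women the standard error is 0.0290. The shift is 0.0105 / 0.0290 = 0.36 standard errors, and type I error is about 0.065.
- Loss of 5% and 10%: 0.20 / 0.90 = 22.2%. With 377 and 357 women the standard error is 0.0301. The shift is 0.0222 / 0.0301 = 0.74 standard errors, and type I error is about 0.11.

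**5. Worst-case bounds.** Take observed rates of 30% and 20%, with equal loss m in both arms and nothing assumed about the women lost.

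- m = 5%: lower 0.285 − (0.190 + 0.05) = +4.5 points; upper (0.285 + 0.05) − 0.190 = +14.5 points.
- m = 10%: lower 0.270 − (0.180 + 0.10) = −1 point; upper (0.270 + 0.10) − 0.180 = +19 points.

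**The case against.** Several parts of the plan suggest that the authorization was meant to come early. Item 6 of the D.4 summary starts every intervention from it. D.6.4 has the nurse review records before calling. Table 7 marks record verification at baseline. The recruitment and consent text in section E mentions the form. This makes the 4-week reading less secure, and it should not be stated as fact. It does not bring signing ahead of disclosure, because D.5 still releases the arm when the baseline survey is completed.

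A reader might infer more than the documents support, in four ways:

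- *That non-signers are excluded from the analysis after randomization.* Item 5 of the D.4 summary is a procedural step. No section removes non-signers from the analysis set, and Program Effectiveness keeps all randomized women.
- *That a record-based outcome is promised outright for dropouts.* Program Effectiveness and the close of the missing-data bullet both make it conditional on the claims data being obtainable. Only the loss-to-follow-up bullet and the signed-consent sentence carry no condition.
- *That the outcome is lost altogether.* Self-report at 6 months is also a source, and the missing-data bullet treats missing only the early follow-up as a separate pattern from missing 6 months. That records cannot be had without this signature is itself an inference: lists with mammogram status are used before any authorization, though no section extends that access to outcomes.
- *That 5% to 10% per arm will be unobtainable, so that bounds 10 to 20 points wide swamp the effects.* Those percentages are total 6-month loss, and women who leave after signing have given access. Even with all of it placed before signing, a 10-point difference keeps its sign at 5% loss. Planned differences from usual care are 10, 20 and 35 points.

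The plan also provides multiple imputation, sensitivity analyses and a comparison of women with and without complete data. These soften the problem but do not restore the missing records.

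**Conclusion.** The concern holds as a conflict of sequence with a possible bias. On either available reading, the release for records is signed after the woman knows her arm. The plan as written can therefore leave randomized women without an authorized record-based outcome, possibly unequally by arm. That contradicts the premise that enrolled women will have signed and the unconditional statement about the records audit. It also weakens the intent-to-treat analysis, which is itself conditional.

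The share affected is unknown. Among women lost to follow-up it is bounded by the plan's own total, 0 to 10% per arm. Within that range the illustrated type I error runs from about 0.065 to 0.11, but only if loss differs by arm and the women lost in the intervention arm are all nonadherent. The documents give no rate to support or refute that. The stated power is not at issue. The change should be made because it removes an avoidable source of bias at small cost.

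**What to change.** - Take the electronic authorization at the end of the baseline survey, and program the system to release the assignment only once it is signed.
- Describe how women who complete baseline by telephone will sign before the assignment is released. At present the only stated signing point is an online questionnaire.
- Rewrite D.4 (text and summary items 4 to 6), D.5, D.7 and D.8 so that they give one order of events and one starting point for delivery. Align the missing-data bullet with it, so that its statement about signed consent is true of every randomized woman.

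The cost is wording, survey programming and one more step before randomization, felt most by telephone completers, who may need a second contact. Women who will not sign are lost before randomization instead of after it. That may reduce enrolment by a number the documents do not allow one to estimate, but it leaves the arms comparable.
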